At Visits 2 and 4 (Week 15 and Week 21, respectively), subjects will return to the study site with all of their used and unused cartridges, which will be counted. Vital signs will be taken and medical history and symptom-driven physical examination will be performed. Compliance with daily tobacco use reporting will be discussed and eCO will be measured; use of non-test product and/or eCO measurements > 5 ppm will prompt counseling by clinic staff on the tobacco and nicotine restrictions and, for measurements > 8 ppm, potential for removal from the study. Test Product for the following 3 weeks and a urine collection container will be dispensed. Subjects will receive reminder calls regarding their following clinic visits and need to collect the first void urine prior to returning to the study site (Visits 3 and 5).

[figure not shown]
At Visit 3 (Week 18), procedures will be as described for Visits 2 and 4 (Weeks 15 and 21, respectively), with the addition of spirometry, questionnaires, and collection of urine and blood for Week 18 biomarkers and future biomarker assessments. A urine collection container will not be dispensed at Visit 3

At Visit 5 (Week 24), subjects will return to the study site with all of their used and unused cartridges (which will be counted), blood and urine samples will be collected for Week 24 biomarker assessments, questionnaires will be completed, and subjects will undergo EOS procedures and be discharged from the study.

All subjects will report their cigarettes per day (Control and Test groups) and Test product use (Test groups only) daily using a SMS, i.e., text message, based system (Med-Quest). The self-reported cigarettes per day (CPD), use of other tobacco products, and measurements of eCO and NNN taken during the in-clinic visits will be used to monitor subject compliance with exclusive use of the Test products. All subjects will return to the study sites for four visits at Weeks 15, 18, 21, and 24.

Throughout this SAP, Screening refers to Visit 1 and/or Visit 2 of the 12-week ALCS-RA-16-06-EV study (CA20130), and study weeks are relative to Week 1 (Visit 3) of the 12-week ALCS-RA-16-06-EV study. Baseline values reported on Day 1 (Week 1) or at Screening (for spirometry only) of the 12-week ALCS-RA-16-06-EV study (CA20130) will be used, except for product use. Baselines for product use will be defined in the product use sections.

The overall design of the study is shown below.

BOE: Biomarker of Exposure

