4. ANALYSIS POPULATIONS

The Clinical Safety Population (CSP):

The CSP will consist of all subjects who are enrolled into this study and record at least one use of study products (i.e., conventional cigarettes or test e-vapor products) after Week 12.

The Modified Intent-to-Treat (mITT) Population:

The mITT population includes those subjects in the CSP population for which there is a baseline for a primary biomarker and at least one post-baseline biomarker measure for the primary biomarker after Week 12.

The Per-Protocol (PP) Population:

The PP population will be a subset of the mITT Population, which is comprised of subjects who completed the study without any major protocol violations, which are defined as:

- Control group: subjects who quit cigarette smoking (either by self report or NNN criteria of $\geq 80\%$ reduction in NNN from baseline at Visit 3 or 5).
- Test groups: subjects who self-report use of $> 10\%$ of baseline CPD over the course of the study*, subjects with an eCO > 8 ppm at any one visit in Visits 2 - 5, or subjects whose NNN levels are consistent with smoking cigarettes (ie, $< 80\%$ reduction in NNN from baseline) at Visit 3 or 5, and subjects who used ≤ 2 cartridges per week during any given week from Weeks 13 to 24.

*Baseline is defined as the CPD reported at Screening (Visit 2) of the 12-week ALCS-RA-16-06-EV study (CA20130), and the course of the study (post baseline) is defined as the average number of cigarettes smoked from Day 1, Week 1 of ALCS-RA-16-06-EV through the end of Week 24.

The CSP and PP populations will be used for the analyses of subject demographics, baseline characteristics and tobacco product use.

The mITT and PP populations will be used for the analyses of the primary endpoint. All other endpoints (excluding demographics, baseline characteristics, and safety data) will be analyzed based on the mITT population concept defined for each endpoint that includes subjects who has a baseline value and at least one post-baseline value. A PP population will be applied to the spirometry dataset using the criteria listed above.

The CSP will be used for the analyses of AEs, vital signs, clinical laboratory findings and other study safety related variables.

If it is determined that a subject was pregnant during the study, all of the pregnant subject's safety and biomarker data will be reported, but will be excluded from the biomarker summarization and statistical analyses.

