5. STUDY GROUP AND PRODUCT DESCRIPTIONS

The following products will be tested in this study:

- Product A = Test EVP (currently marketed by Nu Mark LLC as MarkTen® XL Bold Classic [4.0% NBW]) [CVR2.6.8] Formula: 10381-44-B; Name: "Rosetta"; Label: B44 (Product XLCB)
- Product B = Test EVP (currently marketed by Nu Mark LLC as MarkTen® XL Bold Menthol [4.0% NBW]) [CVR2.6.8] Formula: 10381-40-E; Name: "Spencer"; Label: 40E (Product XLMB)

The following groups will be tested in this study:

Test 1 Group: Exclusive ad libitum use of test e-Vapor Product XLCB, without use of any other type of tobacco/nicotine containing product, for the entire additional 12 weeks

Test 2 Group: Exclusive ad libitum use of test e-Vapor Product XLMB, without use of any other type of tobacco/nicotine containing product, for the entire additional 12 weeks

Test 1 + Test 2 Group = Combined e-vapor use group

Control Group : Continue smoking under ad libitum use of subjects' own brand of conventional lit-end cigarettes, without use of any other type of tobacco/nicotine containing product, for the entire additional 12 weeks

The following study group descriptions will be used in the footnotes for listings, tables, and figures.

Test 1 Group = e-Vapor Product XLCB

Test 2 Group = e-Vapor Product XLMB

Test 1 + Test 2 Group = Combined e-Vapor Use Group

Control Group = Continue smoking lit-end conventional cigarette

Study groups will be referred to in the text as: Test 1 Group, Test 2 Group, Combined Test Group, and Control Group.

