6.1.3 Product Use and Compliance Data Collection and Analysis Variables

6.1.3.1 Data Collection

Product use (number conventional cigarettes used, number test e-vapor cartridges started, and number of puffs taken using the test products, either ≤ 20 or > 20) will be reported daily using a short message service. Exhaled CO (eCO) measurements will be performed by the clinic staff using the Micro+ basic™ Smokerlyzer® monitor (coVita) at Visits 3, 4, and 5. Use of other tobacco products will also be recorded at Visits 3, 4, and 5. Urine will be collected for determination of NNN at Visits 3 and 5.

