6.1.3.2 Analysis Variables

- Average number of cigarettes per day by week
- Average number of e-vapor cartridges started per day by week
- Frequency and percentage of subjects with a reduction, no change, or increase in cigarettes used per day from Baseline (the cigarettes per day reported at Screening, Visit 2 of the 12-week ALCS-RA-16-06-EV study) to Visit 5 (Week 24)
- Frequency and percentage of subjects with a reduction, no change, or increase in e-vapor cartridges used per day from Baseline (the average e-vapor cartridges started per day during Week 1 of the 12-week ALCS-RA-16-06-EV study) to Visit 5 (Week 24)
- Measured eCO determined at Baseline, Visit 2, Visit 3, Visit 4, and Visit 5 (Week 24)
- Use of Other tobacco products (yes/no)
- Creatinine-adjusted urine NNN determined at Baseline*, Visit 3, and Visit 5 (Week 24) (calculated as described in Section [6.1.1.3.2](#))

*Baseline values reported on Day 1 (Week 1) of the 12-week ALCS-RA-16-06-EV study (CA20130) will be used.

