14.2.2 Product Use and Compliance Tables

| | |
|------------------|---|
| Table 14.2.2.1.1 | Summary of Average Number of Cigarettes Used Per Day by Study Group and Week (Week 12 through Week 18) |
| Table 14.2.2.1.2 | Summary of Average Number of Cigarettes Used Per Day by Study Group and Week (Week 19 through Week 24) |
| Table 14.2.2.1.3 | Summary of Change from Baseline Cigarettes Used Per Day by Study Group and Visit |
| Table 14.2.2.1.4 | Summary of Average Number of e-Vapor Cartridges Started Per Day by Study Group and Week (Week 12 through Week 18) |
| Table 14.2.2.1.5 | Summary of Average Number of e-Vapor Cartridges Started Per Day by Study Group and Week (Week 19 through Week 24) |
| Table 14.2.2.1.6 | Summary of Change from Baseline e-Vapor Cartridges Started Per Day by Study Group and Visit |
| Table 14.2.2.2 | Frequency of Reduction, No Change, or Increase in Cigarettes Per Day and e-Vapor Cartridges Started Per Day from Baseline to Week 12 by Study Group |
| Table 14.2.2.3.1 | Frequency of Subject Days with \leq 20 or $>$ 20 Puffs per Day for e-Vapor Products by Study Group and Week (Week 12 through Week 18) |

| | |
|------------------|--|
| Table 14.2.2.3.2 | Frequency of Subject Days with \leq 20 or $>$ 20 Puffs per Day for e-Vapor Products Study Group and Week (Week 19 through Week 24) |
| Table 14.2.2.4.1 | Summary of eCO (ppm) by Study Group and Visit |
| Table 14.2.2.4.2 | Summary of urine NNN (ng/g Cr) by Study Group and Visit (mITT population) |
| Table 14.2.2.4.3 | Summary of urine NNN (ng/g Cr) absolute change from Baseline by Study Group and Visit (mITT population) |
| Table 14.2.2.4.4 | Summary of urine NNN (ng/g Cr) percent change from Baseline by Study Group and Visit (mITT population) |
| Table 14.2.2.4.5 | Frequency of eCO and Urine NNN by Study Group and Visit |

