Appendix 16.2.6.8.1 Product Used Per Day

| Subject Number | Study Group | Study Day | Date | Number of Cigarettes Smoked | Use of other Tobacco Products |
|----------------|-------------|-----------|----------|-----------------------------|-------------------------------|
| XXXXXX | XXXXX | X | DDMMYYYY | XX | Yes No |

Note: Test 1 Group = e-Vapor Product XLCB
Test 2 Group = e-Vapor Product XLMB
Control Group = Continue smoking lit-end conventional cigarette

Program: /CAXXXX/sas_prg/stsas/lis_PROGRAMNAME.sas DDMMYYYY HH:MM

Programmer Note: Please include Baseline CPD (Screening value from ALCS-RA-16-06-EV study CA20130)

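### The per-protocol violation list omits use of other tobacco or nicotine products, which the SAP bars in every group and records; separately, some cigarette-count labels are wrong (minor)

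*SAP*

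**What the plan says.** **PP set.** Section 4 limits PP to mITT subjects who completed without a major violation, and then defines those violations. For Control the item is "Control group: subjects who quit cigarette smoking (either by self report or NNN criteria of" at least an 80% reduction in NNN at Visit 3 or 5. For the Test groups the items are self-reported CPD above 10% of baseline, eCO above 8 ppm at any of Visits 2 to 5, an NNN reduction below 80% at Visit 3 or 5, and two or fewer cartridges in any of Weeks 13 to 24.

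**Other products.** Section 5 describes Control as continued smoking of the subject's "own brand of conventional lit-end cigarettes, without use of any other type of tobacco/nicotine containing product, for the entire additional 12 weeks". Test 1 is "Exclusive ad libitum use of test e-Vapor Product XLCB, without use of any other type of tobacco/nicotine containing product", and Test 2 carries the same restriction. Section 3 names several monitoring measures, daily cigarette counts among them: "use of other tobacco products, and measurements of eCO and NNN taken during the in-clinic visits will be used to monitor subject compliance". The compliance meant there is that Test subjects keep to their assigned product alone. Section 6.1.3.1 states "Use of other tobacco products will also be recorded at Visits 3, 4, and 5". Section 6.1.3.2 includes "Use of Other tobacco products (yes/no") among the analysis variables. The listing shell for Appendix 16.2.6.8.1 has a column "Use of other Tobacco Products" by study day. The only compliance frequency table in the 14.2.2 list is "Frequency of eCO and Urine NNN by Study Group and Visit".

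**CPD labels.** Sections 4, 6.1.3.2 and 6.2.5 take baseline CPD from Screening Visit 2. Tables 14.2.2.1.1, 14.2.2.1.3 and 14.2.2.2 and Appendix 16.2.6.8.4 print Visit 1. The footnote to Table 14.2.2.1.3 defines its Weeks 1-24 column as an average over Weeks 12-24. The table list ends Table 14.2.2.2 at Week 12, while its shell says Week 24. Section 6.1.3.1 omits Visit 2 from the eCO visits.

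**The concern.** The SAP treats use of other products as non-adherence in its group descriptions and collects data on it, but does not use those data where adherence decides who is analysed. PP and mITT are both used for the primary endpoint, and the PP criteria are also applied to spirometry. Of the two primary sets, only PP is built on adherence. If the plan is followed exactly, a subject recorded as using a barred product can count as having no major violation. In Control this could blur the contrast between continued smoking and switching, since the added product may itself be an e-vapor product.

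The label errors are a smaller matter. Taken literally, they could put a wrong CPD percent change, or a wrong reduction / no change / increase category, into the tables. That category is a listed secondary outcome.

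**Working it through.** The SAP gives no figure to reproduce on this point. The check follows subjects through the rules, then sizes the effect under stated assumptions.

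**1. Control subject who still smokes and records Yes for another product.** The only item is quitting, by self-report or NNN. The subject has not quit, so no item applies and the subject stays in PP.

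**2. Test subject who records Yes.** The CPD item counts cigarettes only. The cartridge item sets a minimum, so added products do not trigger it. The eCO and NNN items are aimed at smoking: Section 4 describes the failing NNN level as one consistent with smoking cigarettes. Some other tobacco use may trip them. A non-test e-vapor product need not, because footnote c of Section 2.1.1 treats NNN consistent with switching to an e-vapor product as acceptable.

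**3. Where the variable appears.**
- Barred: Sections 3 and 5, all groups.
- Recorded: Section 6.1.3.1, by visit.
- Analysis variable: Section 6.1.3.2.
- Listed: Appendix 16.2.6.8.1, by study day.
- Summarised: Section 6.2.5 in general terms (frequency counts for categorical product-use data), with no table in the 14.2.2 list.
- PP rule: absent.

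The by-visit and by-day records disagree. The daily text-message items in Section 6.1.3.1 are cigarettes, cartridges and puffs, so the daily record rests on the listing shell alone.

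**4. Size in Control.** Shift in the Control mean = (k/n) × d, where k is the number of such subjects kept in, n the group size and d the mean change the use causes in them. With n = 52 enrolled (Section 3) and k assumed from 1 to 5:
- 1/52 = 1.9% of d
- 5/52 = 9.6% of d

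The SAP gives neither k nor d. PP Control can be no larger than 52, so for a given k these shares are lower bounds.

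**5. Precision cost of excluding them.** Interval width scales as 1/√(1 − f) if a fraction f is removed from each group. For assumed f:
- f = 0.05: 1/√0.95 = 1.026
- f = 0.10: 1/√0.90 = 1.054

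**6. Averaging footnote, Table 14.2.2.1.3.** Assume baseline 20 CPD, 5 CPD in Weeks 1-11, then none. The Weeks 1-24 mean is 5 × 11/24 = 2.29, or 11.5% of baseline, a change of −88.5%. The Weeks 12-24 mean is 0, a change of −100%. With 3 to 8 CPD in Weeks 1-11, the correct change runs from −93.1% to −81.7%, and the footnote's window still gives −100%.

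**7. Baseline visit label.** Assume Week 24 CPD of 18 and a Visit 1 value of 20: 18/20 − 1 = −10%, a reduction. With a Visit 2 value of 18 the result is no change; with 15 it is 18/15 − 1 = +20%, an increase. This matters only if CPD was recorded separately at the two visits.

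**The case against.** The closed list looks deliberate, and whether other-product use is a major violation is partly judgement. The monitoring sentence in Section 3 concerns exclusive use of the test products, so it bears on the Test groups, where eCO and NNN already act. Section 3 also has non-test product use prompt counselling, and the SAP provides a listing of protocol deviations. The shells are declared open to change. All of this is fair, but counselling and listings do not alter PP membership, and nothing in the SAP explains why a barred and recorded behaviour is left out.

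Four stronger readings are tempting, and the SAP does not support them.
- *PP is the primary analysis set.* Sections 4 and 6.3.1 use both mITT and PP, and the mITT result does not depend on these criteria. The link between PP and the complete switching of footnote c is an inference; the SAP does not state it.
- *No summary of other-product use is planned.* Section 6.2.5 plans one in general terms. What is missing is a table to carry it.
- *A tolerance of more than 10% of days would match the CPD rule.* That rule is a share of baseline cigarette quantity averaged over Weeks 1 to 24. A count of days in Weeks 13 to 24 differs in unit and window, and would rest on a daily record shown only in a listing shell.
- *The Visit 1 label certainly changes results.* The SAP does not show that two screening CPD values exist.

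**Conclusion.** The point holds. The PP definition omits other-product use in every group. The gap is clearest in Control, where no other item can catch it; in the Test groups eCO and NNN may catch some but not all of it. The consequence is that a subject recorded as non-adherent stays in one of the two primary-endpoint sets. How much this matters cannot be known from the SAP: the 1.9% to 9.6% range rests on an assumed 1 to 5 of 52 Control subjects and is relative to an unknown effect.

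The label errors are a separate, minor point. The averaging footnote would give a wrong figure whenever mean CPD over Weeks 12-24 differs from that over Weeks 1-24; the visit label does so only conditionally. A reader might infer that they also distort PP. They do not, because Section 4 carries its own correct baseline and window.

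**What to change.** **Main change.**
- In Section 4, add any Yes recorded for other tobacco or nicotine product use at Visits 3, 4 or 5 as a PP violation in the Test and Control groups. Fix it before database lock and without reference to biomarker results; this matters because the study is open-label and enrolment numbers are already in the SAP.
- Reconcile Section 6.1.3.1 (by visit) with Appendix 16.2.6.8.1 (by study day).
- Add other-product use (yes/no) by group to the compliance frequency table. It is 14.2.2.4.5 in the table list, but its shell is numbered 14.2.2.4.3; align the two.

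**Minor change.** Align the shells with Section 6.2.5:
- define the Weeks 1-24 column of Table 14.2.2.1.3 as the average over Weeks 1-24;
- set the CPD baseline to Screening Visit 2 in Tables 14.2.2.1.1, 14.2.2.1.3 and 14.2.2.2 and Appendix 16.2.6.8.4;
- change the listed title of Table 14.2.2.2 to Week 24.

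Also bring the eCO visits in Section 6.1.3.1 into line with Sections 3, 4 and 6.1.3.2, which include Visit 2.

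**Cost.** Wording, one added table item and a somewhat smaller PP set. The data are already collected.

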6. BIOMARKER, PRODUCT USE, PULMONARY FUNCTION, AND QUESTIONNAIREASSESSMENT AND ANALYSIS

6.1 Biomarkers Sample Collection and Measurements

6.1.1 Urine Biomarkers of Exposure and Biomarkers of Potential Harm

6.1.1.1 Urine BOE and BOPH Sample Collection

The first urine void of the day will be collected by the subjects and brought to the study sites on Visit 3 and Visit 5. Aliquots will be taken for analysis of urine NE (nicotine, nicotine glucuronide, cotinine, cotinine glucuronide, trans-3'-hydroxycotinine, and trans-3'-hydroxycotinine glucuronide), total NNAL, NNN, 11-dehydrothromboxane B₂, and 8-epi-prostaglandin F_{2a}, and creatinine. The remaining volume will be used for bio-banking.

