6.2.5 Product Use and Compliance

Product Use

The number of cigarettes smoked per day, number of new e-vapor cartridges started per day, and number of puffs taken using test products (≤ 20 puffs or > 20 puffs) will be listed by subject and study day. Continuous variables will be summarized by descriptive statistics while categorical data will be presented using frequency count table. The average number of cigarettes smoked per day and e-cartridges started per day will be summarized by group and Week (Weeks 12 through 24) using descriptive statistics (number of observations [n], number of missing values [n missing], arithmetic mean [mean], standard deviation [SD], coefficient of variation [CV%], standard error of the mean [SEM], minimum, Q1, median, Q3, maximum and 95% CI). The overall average for Weeks 12 through 18 and Weeks 24 through 24 and Weeks 1 through 24 (CPD only for Weeks 1-24) will be presented. The percent change from Baseline to Week 18, Week 24, and Weeks 1-24 (CPD only for Weeks 1-24) will be calculated, where:

- Baseline for CPD is defined as the CPD reported at Screening, Visit 2 of the 12-week ALCS-RA-16-06-EV study;
- Baseline for the test products is defined as the average of Week 1 of the 12-week ALCS-RA-16-06-EV study;
- Week 18 is defined as the average of Week 18;
- Week 24 is defined as the average of Week 24;
- Weeks 1-24 is defined as the average of Weeks 1-24.

Frequency tables (n, %) will also be used to summarize the proportions of subjects in the following percent change categories: reduce, no change, or increase from Baseline to Week 24 for each study group.

Compliance

ECO concentration, creatinine-adjusted NNN concentration, and absolute and percent change from baseline in creatinine-adjusted NNN concentration will be listed by

subject and study day. Frequency tables (n and %) will be used to summarize eCO (≤ 5 , >5 to ≤ 8 and >8 ppm) and NNN (< 80% reduction from baseline or $\geq 80\%$ reduction from baseline) for assessment of compliance and noncompliance for each study group.

Analysis of NNN will be performed on the mITT population. Other product use and compliance variables will be summarized using available data.

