Appendix 16.2.5.2.2 Confirm Regular Cigarette Brand

| Subject Number | Visit | Study Group | Has the Subject's Regular Brand of Cigarettes (Control group) Changed? | If Changed, Was New Cigarette Pack Photocopied? |
|----------------|-------|-------------|--|---|
| XXXXXX | XXXXX | X | XXX | XXX |

Note: Test 1 Group = e-Vapor Product XLCB
Test 2 Group = e-Vapor Product XIMB
Control Group = Continue smoking lit-end conventional cigarette

Program: /CAXXXX/sas_prg/stsas/lis_PROGRAMNAME.sas DDMMMYYYY HH:MM

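### The per-protocol Control criterion can exclude a continuing smoker as having quit on one low urine NNN, even when self-report and an eCO above 8 ppm at that visit show smoking

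*SAP*

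**What the plan says.** SAP Section 4 lists the major protocol violations that remove a subject from PP.

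- **Control:** "Control group: subjects who quit cigarette smoking (either by self report or NNN criteria of" a fall of at least 80%, completed by "reduction in NNN from baseline at Visit 3 or 5". The two triggers are alternatives, and so are the two visits.
- **Test groups:** the list includes "subjects with an eCO > 8 ppm at any one visit in Visits 2 - 5" and "subjects whose NNN levels are consistent with smoking cigarettes", the latter meaning a fall of less than 80% at Visit 3 or 5. No eCO term appears for Control.

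The evidence that could check an NNN-based quit label is collected in Control:

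- Section 3: "All subjects will report their cigarettes per day (Control and Test groups" being included, by daily text message.
- Section 6.1.3.1: eCO is measured at Visits 3, 4 and 5.
- Section 6.2.5: eCO and NNN categories are tabulated "for assessment of compliance and noncompliance for each study group". The shell for the eCO and NNN frequency table has Control rows for both.

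On the urine samples, Section 6.1.1.1 states "The first urine void of the day will be collected by the subjects and brought to the study sites on Visit 3 and Visit 5". NNN and total NNAL are both assayed from that void, and Section 6.1.1.3.2 divides both by urine creatinine. Change in creatinine-adjusted total NNAL to Week 24 is a primary outcome (Section 2.2), analysed on mITT and PP (Sections 4 and 6.3.1).

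**The concern.** The Control arm is asked to go on smoking, so its violation is having stopped. A Control who texts daily cigarettes and blows an eCO above 8 ppm at Visit 5 is doing what the arm requires. If that visit's NNN is at least 80% below the single Day 1 value, the subject is nevertheless removed as a quitter. A chance-high baseline or one unusually low sample could produce this.

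The SAP does not otherwise accept an NNN fall alone as proof of not smoking. The footnote to the primary objective (Section 2.1.1) defines complete switching by exclusive e-vapor use, eCO of 8 ppm or less and consistent NNN together.

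Two things are at stake. Compliant Controls can be misclassified. And the PP set is selected on a post-baseline marker measured in the same sample as a primary outcome, in the direction that favours the test products.

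**Working it through.** **1. The two rules side by side.** Take the same illustrative findings at Visit 5 in each arm: NNN down 85%, eCO 25 ppm.

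| Arm | Criterion met | Reading | PP status |
|---|---|---|---|
| Test | eCO > 8 ppm | smoking | excluded |
| Control | NNN fall of at least 80% | quit | excluded |

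Identical evidence gets opposite labels. Reported cigarettes do not change the Control outcome.

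**2. How often could an unchanged smoker be flagged?** The SAP gives no NNN variability and no expected exclusion rate, so there is no plan figure to reproduce.

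Inputs from the SAP: 52 Controls (Section 3); trigger ratio of 0.20 or less, ln 0.20 = −1.609; two visits sharing one baseline.

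Assumptions: creatinine-adjusted NNN is log-normal with within-subject log SD *s*; Baseline, Visit 3 and Visit 5 are independent within a person; there is no true change.

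- One visit: P = Φ(−1.609 / (*s*√2)). For *s* = 0.5: −1.609/0.707 = −2.276, P = 1.1%. For *s* = 0.7: −1.609/0.990 = −1.626, P = 5.2%.
- Either visit: bivariate normal with correlation 0.5, because the baseline is shared.

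| *s* | One visit | Either visit | Expected of 52 |
|---|---|---|---|
| 0.4 | 0.2% | 0.4% | 0.2 |
| 0.5 | 1.1% | 2.1% | 1.1 |
| 0.7 | 5.2% | 9.1% | 4.7 |
| 0.9 | 10.3% | 17.2% | 9.0 |
| 1.1 | 15.0% | 24.3% | 12.6 |

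**3. What this does to Control NNAL.** Simulation of 400,000 unchanged smokers, with NNAL within-subject log SD 0.4 or 0.6 and within-visit NNN–NNAL error correlation ρ. Entries are the upward shift in the retained Controls' mean NNAL change, adjusted for baseline NNAL, as a percentage of the baseline mean.

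| *s* | ρ = 0 | ρ = 0.3 | ρ = 0.6 |
|---|---|---|---|
| 0.4 | about 0 | about 0.2 | 0.3–0.4 |
| 0.5 | about 0 | 0.6–0.7 | 1.3–1.5 |
| 0.7 | about 0 | 2.0–2.5 | 4.2–5.1 |
| 0.9 | about 0 | 3.4–4.3 | 6.9–8.5 |
| 1.1 | about 0 | 4.6–5.7 | 9.3–11.2 |

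For positive ρ the shift is always upward. If NNAL falls in the Test groups, that widens the Test-minus-Control difference. The shared void and divisor make a positive ρ plausible at Visits 3 and 5. The model assumes the same at Baseline, which was collected in the earlier study and is not described here.

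**4. Against sampling error.** A second simulation used NNAL log SD 0.4 and ρ from 0.5 to 0.8. The shift in mean log NNAL change was 0.012–0.019 at *s* = 0.5, 0.025–0.041 at *s* = 0.6 and 0.056–0.090 at *s* = 0.8. The SD of a change is 0.4√2 = 0.566. With 52 Control and 50 Test 1 subjects, the SE of a difference is 0.566 × √(1/52 + 1/50) = 0.112. The shifts are therefore about 0.1–0.4 SE at *s* = 0.5–0.6 and 0.5–0.8 SE at *s* = 0.8.

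**The case against.** **Any single sign excludes in both arms.** In the Test groups, too, self-report, eCO or NNN alone suffices, with the same 80% cut-off. Asking for agreement only in Control looks like a new asymmetry. This does not stand. Each of those three Test criteria is a sign of smoking, and smoking is the Test violation, so one sign can reasonably be enough. The Control violation is having stopped, and an eCO above the SAP's own limit at the same visit contradicts it directly.

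**The effect may be small and is visible.** This stands as a limit on scope. The same model is run on mITT, which does not use the rule, and both NNAL results are tabulated. Per-subject listings show eCO, daily cigarettes and NNN category, and Appendix 16.2.3 lists exclusions. Section 3 calls the analysis mostly exploratory. On much of the assumed range the shift is well under one standard error.

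**Stronger readings that the SAP does not support.** A reader might infer that the rule removes Controls with low nitrosamine levels. It does not: it acts on a fall from the subject's own baseline. A Control with steadily low NNN stays in, while one low Visit 3 value excludes a subject whose Week 24 NNN is back at baseline. A reader might also take the listing that asks "Has the Subject's Regular Brand of Cigarettes (Control group) Changed" as showing that brand changes are expected and explain such falls. It shows only that a change is recorded; nothing in the SAP links brand to an 80% NNN fall.

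**Conclusion.** The criterion is wrong as drafted: it can label a documented smoker as having quit, on evidence that the SAP's own Test criterion reads as smoking. That follows from the text and needs no assumption.

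The consequence for NNAL is conditional. A reader might infer that the PP contrast is inflated. The SAP supports only that it can be, because it gives no NNN or NNAL variability and no correlation between them. Under the assumptions shown, the upward shift in Control NNAL change is negligible at *s* = 0.4 or ρ = 0, and about 4–5% of baseline at *s* = 0.7 with ρ = 0.6. It reaches about 11% only at the far corner of the range. Only PP analyses are affected. The rule should be changed, given how little that costs, but it does not undermine the mITT result.

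**What to change.** Replace the Control criterion in Section 4 with: *subjects who quit cigarette smoking, by self-report, or by a reduction of at least 80% in creatinine-adjusted NNN from baseline together with eCO of 8 ppm or less at the same visit (Visit 3 or 5)*. Add how a missing eCO at that visit is handled.

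At minimum, keep the rule and add a PP sensitivity analysis of the primary biomarkers that retains Controls flagged by NNN alone.

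The cost is one sentence, or one extra run of an existing model; eCO is already collected at both visits. With the new wording, no Control with eCO above 8 ppm at the flagged visit is dropped on that visit's NNN. Two limits remain. A Control who has largely stopped but has eCO above 8 ppm at that visit would be kept, and how often that would happen cannot be judged from the SAP. A reporting smoker whose eCO is 8 ppm or less would still be excluded, which the sensitivity analysis would cover.

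Requiring the NNN fall at both visits is a weaker alternative. Expected false flags among 52 unchanged smokers drop from 0.2, 1.1, 4.7, 9.0 and 12.6 to about 0.01, 0.1, 0.7, 1.8 and 3.0 for the five values of *s* above, but contrary eCO is still ignored.
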